4.4.2. PROMIS SD SF 8b

• Absolute values and changes from baseline in the PROMIS SD SF 8b total T- and raw scores over time

Details on this instrument can be found in Section 6.1.2.

The absolute values and the change from baseline in the PROMIS SD SF 8b total T- and raw scores over time will be summarized by week and treatment group using descriptive statistical methods as described in Section 4.1.

4.4.3. MenQoL

• Mean change in MENQOL domain and single item scores from baseline over time

Details on this instrument can be found in Section 6.1.3.

The absolute values and the change from baseline will be summarized by week and by treatment group using descriptive statistical methods as described in Section 4.1. The change from baseline over time of domain scores will be shown using line plots for means together with 95% CIs by treatment group. Converted scores will be shown in the tables.

4.4.4. Insomnia Severity Index (ISI)

• Absolute values and changes in the ISI total score over time

Details on this instrument can be found in Section 6.1.4.

version 3.0 Page: 48 of 87

The absolute values for the total score and the change from baseline will be summarized using descriptive statistical methods as described in Section 4.1 by week and treatment group. In addition, Severity of insomnia presented in categories (i.e. "No clinically significant insomnia", "Subthreshold insomnia", "Clinical insomnia (moderate severity)" and "Clinical insomnia (severe)" as defined in Section 6.1.4) will be summarized with frequency tables by treatment group, as well as change from baseline to each week will be described using shift tables.

4.4.5. European Quality of Life 5-dimension 5-level questionnaire (EQ-5D-5L)

• Absolute values and change in EQ-5D-5L single dimensions and health state VAS score over time

Details on this instrument can be found in Section 6.1.5.

The answers to the 5 dimensions will be summarized in frequency tables by week and by treatment group. The change from baseline will be described using shift tables. The health state VAS values and the change from baseline will be analyzed using descriptive statistical methods as described in Section 4.1 by week and treatment group.

Hebrew EQ5D-5L VAS scale was reversed for 12 subjects. They are included in the planned analysis, but sensitivity analysis will be performed, where those 12 subjects will be excluded.

4.4.6. Short Form-36 Health Survey Acute (SF-36 Acute)

• Absolute values and changes from baseline in SF-36 acute domain, physical component summary (PCS) and mental component summary (MCS) scores over time

Details on this instrument can be found in Section 6.1.6.

Each domain a raw score, a standardized score and PCS and MCS scores, as well as change from baseline, will be summarized using descriptive statistics by treatment group and by week.

4.4.7. Beck Depression Inventory (BDI-II)

• Absolute values and changes in the BDI-II total score over time

Calculation of the BDI-II total score is described in Section 6.1.7. The absolute values and the change from baseline will be summarized using descriptive statistical methods as described in Section 4.1 by week and by treatment group. The change from baseline in categories from BDI-II total score (0-13: none to minimal depression, 14-19: mild depression, 20-28: moderate depression and 29-63: severe) will be described using a shift table.

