# 4. Study Design

# 4.1 Overall Design

This is a multi-center, multi-country, double-blind, randomized, parallel-group, placebo-controlled, Phase 3 intervention study in women with, or at high risk for developing hormone-receptor positive breast cancer.

Main study (part A+B): The study includes a wash-out period (if applicable), approximately 6-week screening, a 52-week treatment and a 4-week follow-up period.

Treatment extension (part C): Participants who completed the 52 weeks treatment phase are offered to continue treatment for 2 additional years.

See country-specific requirements for Italy (ITA-1) in Section 10.8.1.1.

**Wash-out:** After giving informed consent, participants will be withdrawn from prohibited concomitant medications (see Section 10.6) at Pre-SCR visit if needed.

10 MAY 2023 Page: 25 of 97

**Screening**: The screening period starts at SCR-1 Visit. The screening period may also be used to obtain a mammogram, if required.

**Randomization**: After screening, eligible participants will be randomized with a 2:1 ratio in a stratified way into 2 arms, as depicted below.

- elinzanetant
- placebo for 12 weeks, followed by elinzanetant for 40 weeks

The randomization will be stratified by women with breast cancer or high-risk for developing breast cancer and by type of treatment for the pre-existing condition at baseline (participants on tamoxifen and participants on aromatase inhibitors).

The investigator will receive an email notification if a participant responded to item 9 of the BDI-II 'Suicidal Thoughts or Wishes' with a 2 = 'I would like to kill myself' or a 3 = 'I would kill myself if I had the chance'. If this happens at screening the participant cannot be randomized. If this happens after randomization the participant can continue in the study at the discretion of the investigator. Any suicidal ideation should be reported as an adverse event and treated according to local clinical practice.

**Treatment**: Participants will receive either 120 mg (2x 60 mg soft gel capsules) of elinzanetant or matching placebo orally once daily. More details are provided in Section 6. Participant surveys will be conducted to evaluate their experience with study assessments and overall satisfaction of participating in the study. These surveys will be conducted at timepoints defined in the SoA, and in addition may be conducted throughout the study.

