#### Other Exclusions

- 22. At screening a response of 2 (I would like to kill myself) or 3 (I would kill myself if I had the chance) on BDI-II item 9 (Suicidal thoughts or wishes).
- 23. Clinically relevant recreational/illicit drug or alcohol abuse within 12 months of signing of informed consent.
- 24. Dependent on the investigator, the contract research organisation(s) or Sponsor for education or employment (e.g. family members, employees, people who receive grants/education).
- 25. Known hypersensitivity to elinzanetant or any of the excipients in the formulation.
- 26. Inability to comply with the study procedures for any reason, including the following examples: language comprehension, psychiatric illness, general inability to get to the study site.
- 27. Wish for pregnancy during the study period.

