# 8.2.11 Suicidal thoughts or wishes: Beck's Depression Inventory (BDI-II)

Suicidal thoughts or wishes will be assessed at screening by the BDI-II item 9. For further details regarding the BDI-II, please refer to Section 8.1.1.6.

See Exclusion Criterion 22 for information on when the participant should not be randomized based on suicidal ideation.

The investigator will receive an email notification if a participant responded to item 9 with a 2 (I would like to kill myself) or a 3 (I would kill myself if I had the chance). If this happens after randomization the participant can continue the study at the discretion of the investigator. The investigator has to consider reporting an adverse event based on the clinical presentation. In addition, any suicidal ideation should be treated according to local clinical practice.

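### No table planned in the SAP identifies responses to BDI-II item 9, the protocol's assessment of suicidal thoughts

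*SAP*

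**What the plan says.** **Protocol.** Section 8.2.11 is one of the eleven subsections under Safety Assessments. It opens with "Suicidal thoughts or wishes will be assessed at screening by the BDI-II item 9", then sets up an email alert to the investigator for a response of 2 or 3 and a rule for later responses: "If this happens after randomization the participant can continue the study at the discretion of the investigator". On AE reporting it says "The investigator has to consider reporting an adverse event based on the clinical presentation". Exclusion criterion 22 concerns the same item and bars entry for "At screening a response of 2 (I would like to kill myself) or 3 (I would kill myself if I had the chance) on BDI-II"; Section 5.4 does not allow rescreening after failure on that criterion. The schedules of activities place the BDI-II at SCR-2 and then at Weeks 4, 8, 12, 16, 26, 36, 52 and 56. It is not scheduled at the baseline visit.

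Protocol 4.1 covers the same item 9 responses but ends differently: "Any suicidal ideation should be reported as an adverse event and treated according to local clinical practice".

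**SAP.** Section 4.4.7 is part of the exploratory endpoints. Its one endpoint is "Absolute values and changes in the BDI-II total score over time". A shift table with four bands is added to show "The change from baseline in categories from BDI-II total score". Section 6.1.7 names suicidal thoughts only as one of the 21 items. Section 4.5.3 (additional safety assessments), the AESI definitions in 4.5.2 and 6.6, the subgroup analyses in 4.6.2 and both versions of the SAP supplement contain no item 9 or suicidality output.

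**The concern.** Ten of the eleven safety assessments in Protocol 8.2 have a matching subsection in SAP 4.5.3. The exception is 8.2.11. Even cervical cytology, which the protocol says is not a safety endpoint, gets a frequency table by treatment group.

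The item is collected repeatedly, including three times in the placebo-controlled period (Weeks 4, 8 and 12), with a planned 270 women on elinzanetant and 135 on placebo. A count by arm of women who answer 2 or 3 after entry is therefore available from data in hand. Without it, what the report says about suicidal ideation depends on two indirect sources: a total score in which item 9 is one of 21 components, and AE reports made under instructions that disagree. A reader of the report could not tell how many women gave such an answer, or in which arm.

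**Working it through.** The plan states no figure for this point, so there is none to reproduce. The check asks whether the planned total-score outputs could reveal a change on item 9.

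**Inputs**
- Each item is scored 0 to 3, and the total is the sum of 21 items (SAP 6.1.7). Check: 21 × 3 = 63, the stated maximum.
- The shift-table categories are 0–13, 14–19, 20–28 and 29–63 (SAP 4.4.7).
- Planned arm sizes are 270 and 135 (SAP 5).
- The total-score email notification is triggered above 19 (Protocol 8.1.1.6).

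**Shift table.** Take a woman with item 9 = 0 at baseline. The other 20 items can sum to anything from 0 to 20 × 3 = 60, which gives 61 possible totals. Let item 9 rise to 3 with the other items fixed, so the total T becomes T + 3. The category changes only if T is within 3 points below a boundary:
- 11, 12, 13 become 14, 15, 16
- 17, 18, 19 become 20, 21, 22
- 26, 27, 28 become 29, 30, 31

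That is 9 totals, so the category is unchanged for 61 − 9 = 52 of 61. Within the lowest category, totals 0 to 10 stay put (11 of 14). For a rise from 0 to 2, only 12–13, 18–19 and 27–28 cross, so the category is unchanged for 61 − 6 = 55 of 61. Where a boundary is crossed, the table shows a change in depression category and not which item caused it.

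These are counts of possible totals, each taken once. They are not probabilities, because the documents do not give the distribution of baseline totals.

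**Mean total score.** One woman with a 3-point rise moves the arm mean by 3/270 = 0.011 points (elinzanetant) or 3/135 = 0.022 points (placebo), using planned arm sizes. If her other items fall by 3 in sum, her total does not move at all.

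**Total-score notification.** From a baseline total of 16 or less, T + 3 is at most 19 and the notification is not triggered. The separate item 9 alert still is. That alert serves the individual woman; it produces no table.

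**AE route.** Under Protocol 4.1 a case of suicidal ideation would be reported and would enter the TEAE tables of SAP 4.5.2, which are split into Weeks 1–12, 13–26 and 27–52 by study drug. Under 8.2.11 an investigator who considers the response and decides against an AE has complied, and the case does not enter those tables. The AE count therefore depends on which section a site follows; the recorded item 9 response does not.

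**The case against.** The strongest case on the other side is that the SAP does what the protocol asks. Protocol Section 3 names TEAEs, abnormal laboratory values and the Sleepiness Scale as the safety endpoints and lists only the BDI-II total score, as exploratory. Section 8.2.11 opens with assessment at screening; afterwards item 9 works as an alert. The rationale for Amendment 2 says responses of 2 or 3 should be read together with the clinical picture, so relying on judged events may be deliberate. This stands in part: an item 9 table is an addition, not the repair of a promised analysis. But 8.2.11 provides explicitly for responses after randomisation, the item is collected at eight visits after the first dose, and a descriptive count does not displace clinical judgement.

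A second objection is that output specifications are held in separate documents (SAP 1), which were not available, and that the listing rules in SAP 4.1 and 4.1.1 could bring in item-level diary data. That is possible. Item 9 is not named, however, and a listing gives no count by arm. Item-level tables are within this SAP's practice: it plans them for PROMIS items, MENQOL items and EQ-5D-5L dimensions.

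Two stronger readings are tempting but not supported:
- *A woman could move to the top response and leave no trace in any table.* The text permits no identifiable trace, but that outcome is not certain. An AE report, which Protocol 4.1 calls for, would appear in the TEAE tables, and unless other items offset them the 3 points do enter the mean total score.
- *Every later response of 2 or 3 is new on treatment.* Criterion 22 acts on the screening answer only. The BDI-II is next given at Week 4 and recalls two weeks, so a later 2 or 3 is new relative to screening. Onset between screening and first dose is not excluded.

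**Conclusion.** The gap is real and is one of safety reporting. No table described in the SAP identifies item 9 responses. The total-score shift table leaves a 0-to-3 change invisible for 52 of 61 possible baseline totals and unattributable for the other 9, and the mean moves by about 0.01 to 0.02 points per woman. The AE tables cannot be relied on to fill the gap while Protocol 4.1 and 8.2.11 differ.

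This assumes that the other 20 items are unchanged, that arm sizes are as planned, and that the unseen output specifications contain no item 9 table. It does not touch the efficacy conclusions or the alert that protects the individual woman. Counts of 2 or 3 may be small, so the comparison would be descriptive. The change should be made because it is cheap and bears directly on something the protocol chose to screen for.

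**What to change.** Add a subsection to SAP 4.5.3, on the safety analysis set:

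1. Item 9 response (0, 1, 2, 3) by visit and treatment group, number and percentage.
2. Shift from the screening response to the worst post-baseline response, by treatment group.
3. Number and percentage of women with any post-baseline response of 2 or 3: Weeks 1–12 by arm, and Weeks 13–52 on elinzanetant. A footnote should say that the reference is the screening answer, because the BDI-II is not repeated at baseline.
4. A listing of these women with visit, response, treatment at the time and any linked AE.

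Separately, Protocol 4.1 and 8.2.11 must be reconciled on AE reporting of suicidal ideation. Which instruction should prevail is for the sponsor to settle. If sites have already worked under both, the report should say so beside the AE counts.

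The cost is about three descriptive tables and one listing from data already collected. There is no effect on alpha or on participant management. The SAP supplements, which already divide other safety tables at Week 12, show a ready route.

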4.4.8. Bleeding diary

Bleeding diary data will be listed.

version 3.0 Page: 49 of 87

4.5. Safety Analyses

4.5.1. Extent of Exposure

The analyses described in this section will be presented for the SAF and the FAS.

Treatment duration will be defined as the number of days from the day of first study drug intake up to and including the day of last study drug intake and will be summarized using descriptive statistics by treatment group and by study drug. For the display by Week 1-12, the treatment duration ends on the end of treatment phase 1 or on the day of last study drug intake, whatever is earlier. For the display by Week 13-26, the treatment duration starts on the first day of treatment phase 2. For the display by Week 27-52, the treatment duration starts on the Visit T9 + 1. The duration of extension period (Part C) starts on the Visit T13 + 1. (As defined in Section 4.1.2.)

The extent of exposure to elinzanetant will be summarized as the total amount of study drug intake in grams and the average daily dose in mg using descriptive statistics per treatment group.

The compliance (as percentage) will be calculated as:

100 * Number of capsules taken / Number of planned capsules

The number of planned capsules is calculated as:

treatment duration * 2

All capsules, including the placebo capsules, will be counted. For participants who withdraw prematurely from the study drug, compliance will be calculated up to the time of last dose. The compliance will be summarized descriptively by treatment group. In addition, percent of compliance will be categorized into 3 groups, less than 80%, 80 to 120% and greater than 120%, and the categories will be summarized by treatment group and by study drug.

Treatment duration will be presented based on the data collected via the eCRF. If the date for end of exposure is not available in eCRF, the last day of drug intake from eDiary will be used to determine the end of exposure. Extent of exposure and compliance will be calculated and presented based on the ePRO daily instrument 'Study drug intake documentation' and on the eCRF 'Drug Accountability' and 'Drug Exposure' pages. The summaries for treatment duration, exposure and compliance will be presented for weeks 1-12, 13-26, 27-52 and overall, (i.e., for the entire 26 (Part A)/52 (Part B) weeks). Treatment duration, exposure and compliance summaries will be shown separately for Part C.

4.5.1.1. Extent of exposure of adjuvant endocrine therapy

The compliance (%) of adjuvant endocrine therapy will be summarized descriptively by treatment group for weeks 1-12, 13-26, 27-52 and overall. The compliance (as percentage) will be calculated as:

100 * Number of days the medication taken / (Number of available daily diary data with adjuvant endocrine therapy intake during treatment period* Daily dosage during baseline)

During Part C at each visit, the investigator will ask the participant about adherence to the prescribed intake of the adjuvant endocrine therapy (tamoxifen/aromatase inhibitor) during

version 3.0 Page: 50 of 87

the past 6 months by use of a five-point Likert scale: none of the time, a little of the time, some of the time, most of the time, all the time. The intake will be summarized using frequency table by visit.

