The mean change in frequency of nighttime awakenings from baseline over time is based on the number of nighttime awakenings during the previous night that is being assessed every morning as part of the HFDD. The baseline value of the nighttime awakenings will be calculated by averaging the nighttime awakenings from the available days during the 14 days prior to start of treatment to a mean daily frequency as (total number of nighttime awakenings during the 14 days prior to start of treatment) / (total number of available days with morning data). Similarly, the frequency of nighttime awakenings for each week during the treatment period will be calculated using the available data during that particular week and averaged to a mean daily frequency as (total number of nighttime awakenings during that week) / (total number of available days with morning data during that week). In case morning data is missing for more than 2 days within a week, the value for that week will be set to missing and no imputation of missing values will be performed. The mean change from baseline will then be calculated as the difference in the mean daily frequency of nighttime awakening for a given week from the corresponding baseline value. A graphical summary (i.e. cumulative distribution function) with absolute change (0 to 100) in the frequency of nighttime awakenings from baseline on the x-axis and proportion of participants achieving this reduction on the y-axis, by treatment group, for week 4 and 12 will also be provided.

Summary statistics for the frequency of nighttime awakenings as well as the absolute change from baseline will be presented by week and by treatment group. The change from baseline over time in the frequency of nighttime awakenings will be shown using line plots for means together with 95% CIs by treatment group.

Sleep disturbances due to HF are assessed every morning as part of the HFDD. Participants provide a rating of their sleep disturbances due to HF in the previous night as

- 'not at all'
- 'a little bit'
- 'somewhat'
- 'quite a bit'
- 'very much'

version 3.0 Page: 47 of 87

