6.4.4. Interruption or discontinuation in intake of adjuvant endocrine therapy

Interruption or discontinuation in intake of adjuvant endocrine therapy will be defined by comparing tablets taken during baseline for two weeks and at selected weeks as follows:

For participants using tamoxifen: reduction of at least 50% of planned daily dosage (tablets taken during the 14 days prior start of treatment, i.e. during baseline) taken during week1, weeks 3 and 4, weeks 7 and 8 or weeks 11 and 12 compared to baseline.

For participants using aromatase inhibitor: reduction of at least 30% of planned daily dosage (tablets taken during the 14 days prior start of treatment, i.e. during baseline) taken during week1, weeks 3 and 4, weeks 7 and 8 or weeks 11 and 12 compared to baseline.

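### The compliance formula for adjuvant endocrine therapy (SAP 4.5.1.1) divides days by days times dosage, so full adherence reads 100%/dosage and a reduced tablet count per day is not visible

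*SAP*

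**What the plan says.** SAP 4.5.1.1 gives the compliance percentage for adjuvant endocrine therapy. Its numerator is "100 * Number of days the medication taken" and its denominator is "Number of available daily diary data with adjuvant endocrine therapy intake during treatment period* Daily dosage during baseline". The result is summarised descriptively by treatment group for weeks 1-12, 13-26, 27-52 and overall. The section does not state the unit of the dosage. The version history records that this formula was clarified in SAP version 2.0.

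Two neighbouring rules are built differently:

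- Study drug, SAP 4.5.1: "100 * Number of capsules taken / Number of planned capsules". Both sides are in capsules.
- Interruption of endocrine therapy as an intercurrent event, SAP 6.4.4: defined by "comparing tablets taken during baseline for two weeks and at selected weeks", with the baseline amount described as "tablets taken during the 14 days prior start of treatment, i.e. during baseline". Both sides are in tablets.

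Protocol 6.8.1 has background medication recorded daily in the eDiary to week 52. Protocol 5.1 (inclusion criterion 2) and 6.8.1 bar switching or dose modification until Visit T6 (week 12) and allow it afterwards.

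**The concern.** Compliance should be a ratio of like to like, equal to 100% when the plan is followed. Here the numerator counts days and the denominator carries an extra factor, the baseline daily dosage, so the result moves with the size of the regimen as well as with adherence to it.

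The table matters because endocrine therapy causes the symptom under study. A reader will use it to judge whether background therapy was kept up in both arms. It also reaches beyond week 12, whereas intercurrent events are flagged only to day 84 (SAP 4.1.2). A misleading percentage could suggest poor adherence where there was none, or hide a real reduction in tablets.

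**Working it through.** The documents state no compliance figure for endocrine therapy, so there is none to reproduce. The check evaluates the formula directly.

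**Inputs**

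- Period: 84 days, the length SAP 6.4.1 uses for weeks 1-12.
- T = days on which the drug was taken; E = available diary entries; D = baseline daily dosage. The values of T, E and D below are assumptions for illustration.
- D need not be 1. Inclusion criterion 2 sets no dose cap, and Protocol 10.9 (Amendment 1) records that a 20 mg tamoxifen maximum was removed. The documents do not give the distribution of tablets per day.

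**Two readings of the diary count**

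The phrase "Number of available daily diary data with adjuvant endocrine therapy intake during treatment period" can mean:

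- Reading A: entries that record an intake. Compliance = 100 × T / (T × D) = 100/D.
- Reading B: entries available on the intake item. Compliance = 100 × T / (E × D). SAP 4.4.1 uses similar wording, "total number of available days with morning data", for non-missing entries.

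**Results with E = 84**

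The last column has tablets in both parts, 100 × (T × D) / (E × D), assuming the full dose on each day of intake.

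| D (tablets/day) | T | Reading A | Reading B | Tablets over tablets |
|---|---|---|---|---|
| 1 | 84 | 100% | 100% | 100% |
| 1 | 67 | 100% | 79.8% | 79.8% |
| 1 | 42 | 100% | 50% | 50% |
| 2 | 84 | 50% | 50% | 100% |
| 2 | 67 | 50% | 39.9% | 79.8% |
| 2 | 42 | 50% | 25% | 50% |

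**Reduced dose on every day.** Plan of two tablets, one taken daily for 84 days: 100 × 84 / (84 × 2) = 50% under both readings. Two taken daily gives the same 50%. In tablets the values are 100 × 84/168 = 50% and 100 × 168/168 = 100%.

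**Fractional D.** If D is the mean of tablets actually taken over the 14 baseline days and one was missed, D = 13/14, and daily intake then gives 100 × 84 / (84 × 13/14) = 107.7%.

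**Effect on an arm mean.** If a share p of fully adherent participants is on two tablets and the rest on one, the mean is 100(1 − p) + 50p = 100 − 50p. That is 100% at p = 0, 95% at p = 0.1 and 90% at p = 0.2. The documents do not give p.

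**Undocumented days.** With 70 entries and 42 days taken at D = 1, Reading B gives 42/70 = 60%; over all 84 planned days it would be 42/84 = 50%. Days without an entry leave the denominator under both readings.

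**The case against.** The strongest reply is that the formula is loosely worded but harmless. At one tablet a day the dosage factor is 1, and on Reading B, which the SAP's own usage in 4.4.1 supports, missed days lower the percentage as they should. This stands for one-tablet participants on documented days. It does not rescue the formula for any other D, and it leaves a programmer to choose between readings that give 100% and 50% for the same half-adherent woman.

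A reader might infer that the formula can never show non-adherence. The documents do not support that: it is true only under Reading A. A reader might also infer results as low as 5%, from 100/20 if dosage were entered as 20 mg. The only unit the SAP gives for baseline dosage, in 6.4.4, is tablets, so nothing points to entry in mg.

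Nor is this the only view of endocrine-therapy adherence by arm. SAP 4.1.3 plans Kaplan-Meier plots of time to interruption and counts of intercurrent events by week, and SAP 4.3.2 splits hot-flash change by presence or absence of the therapy. None uses this formula. They rest on the 50% and 30% reduction thresholds, however, and do not give a percentage.

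Finally, table specifications sit in separate documents (SAP Introduction), so the programmed table may already be right. The point concerns the SAP text.

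**Conclusion.** The formula is wrong as written. Under either reading, full adherence gives 100%/D instead of 100% unless D is exactly 1, and fewer tablets on a day of intake cannot be seen. That missed days vanish as well holds only on the literal reading.

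The size depends on how many participants have a D other than 1, which the documents do not state. For an individual on two tablets the figure is half what it should be; for an arm mean the shortfall is 50p percentage points under full adherence.

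A reader might take this to touch the efficacy results. It does not: the interruption flag compares tablets with tablets, and neither the primary nor the supplementary estimands use the compliance percentage. Randomisation is stratified by tamoxifen or aromatase inhibitor, so the error is more likely to distort the level in both arms than to create a difference between them. The correction is worth making but is limited to one descriptive table.

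**What to change.** Replace the formula in SAP 4.5.1.1 with:

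100 × tablets taken / (days in the period with available background-medication diary data, whether or not intake was recorded × planned tablets per day)

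and state the following:

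- Dosage is in tablets, and planned tablets per day is the prescribed number rather than the mean taken at baseline.
- For weeks 13-26 and 27-52, the planned number is the one in force at the time, since changes are permitted after Visit T6. Keeping the baseline number would score a participant on a permitted new regimen against her old one.
- For the overall figure, tablets taken and tablets planned are each summed across periods before dividing.
- The number of days without diary data is shown alongside by arm and period, because these days leave the denominator.

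The cost is one SAP formula and the reprogramming of one table. No new data are needed if the diary records tablets, as SAP 6.4.4 already presumes.
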